6.1.1. Study Treatment Application Guidance

Participants should remove Study Cream from the tube and apply the Study Cream with their fingertip in small amounts until all of the areas to be treated are covered by a thin, even film (see Figure 8).

Figure 8: Study Cream Application Using a Fingertip

Source: DermNet New Zealand (www.dermnetnz.org).

In the clinic, the amount of study cream used will be determined by weighing a tube(s) before and after the participant or guardian applies a thin film of study cream to the affected areas.

On the day of a visit, the participant should not apply their morning application of study cream at home; instead, study cream will be applied in the clinic during the visit, under direct supervision of the site staff. The tube will be weighed before and after application to determine the participant's usage.

Application instructions will be provided by the site study staff, and the participants will record their daily applications via a diary card provided at each study visit. Participants must not apply study cream more often than BID. Refer to the Study Reference Manual for participant instructions for handling study cream.

6.2. Preparation, Handling, and Accountability

The investigator or designee must confirm appropriate temperature conditions (both ruxolitinib cream and vehicle cream are to be stored between 15°C and 30°C [59°F-86°F]) have been maintained during transit for all study treatments received and any discrepancies are reported and resolved before use of the study treatment.

Only participants enrolled in the study may receive study cream, and only authorized site staff may distribute study cream. The cream will be applied by the participant or her/his parent/legal guardian. Immediately after application of study cream, the hands should be thoroughly washed with soap and water. Note that the study cream is for exclusive use on the skin. In case of accidental exposure to the eyes or mucous membranes, the cream should be immediately removed from that area and necessary supportive measures taken. Refer to the Study Reference Manual for participant instructions for handling of study cream.

All study treatment must be stored in a secure, environmentally controlled, and monitored (manual or automated) area in accordance with the labeled storage conditions with access limited to the investigator and authorized site staff. Participants should store study cream at ambient temperature conditions.

The investigator or designee is responsible for study treatment accountability, reconciliation, and record maintenance (ie, receipt, reconciliation, and final disposition records). Inventory and accountability records must be maintained and readily available for inspection by the study monitor and are open to inspection at any time by any applicable regulatory authorities. The investigator or designee must maintain records that document the following:

- Delivery of study cream to the study site.
- Inventory of study cream at the site.
- Participant use of the study cream, including tube counts from each supply dispensed.
- Return of study cream to the investigator or designee by participants.

The investigational product must be used only in accordance with the Protocol. The investigator will also maintain records adequately documenting that the participants were provided the specified study cream. These records should include dates, quantities, and any available batch or serial numbers or unique code numbers assigned to the investigational product and study participants.

Completed accountability records will be archived by the site. The investigator or designee will be expected to collect and retain all used, unused, and partially used containers of study cream until verified by the study monitor (unless otherwise agreed to by the sponsor). At the conclusion of the study, the investigator or designee will oversee shipment of any remaining study cream back to the sponsor or its designee for destruction according to institutional SOPs. If local procedures mandate on-site destruction of the investigational supply, the site should (where local procedures allow) maintain the investigational supply until the study monitor inspects the accountability records in order to evaluate compliance and accuracy of accountability by the investigative site. At sites where the study cream is destroyed before monitor inspection, the monitors rely on documentation of destruction per the site SOP.

Further guidance and information for the final disposition of unused study treatments are included in the study materials provided to sites.

6.3. Measures to Minimize Bias: Randomization and Blinding

All participants will be centrally assigned to study treatment using an IRT system. The system will assign in a 2:2:1 ratio, stratified by baseline IGA score (2 or 3) and age, assign the participant study number, track participant visits, randomize according to the defined parameters, maintain the blinding, and manage study cream inventory. Full details will be provided in the IRT Manual. Study treatment will be dispensed at the study visits summarized in the SoA (see [Table 3](#) and [Table 4](#)).

6.4. Study Treatment Compliance

Compliance will be assessed for frequency of administration of study cream by reviewing the participants' diaries. Participants will also be questioned regarding study cream application technique, missed applications, and use of any additional topical or systemic prescriptions of other products or over-the-counter products. Compliance with study cream will be evaluated by the participant's adherence to the BID application regimen (evaluation of actual number vs prescribed number of applications) and documented by the site staff and monitored by the sponsor/designee.

Qualified clinical staff will review the diary entries for compliance. Participants will be considered compliant with the treatment regimen if they apply at least 80% but no more than 120% of the prescribed number of applications during participation in the VC period of the study. Participants who are noncompliant during the VC period and LTS period (if on a treatment cycle) will be reinstructed by the investigator (or designee), and the sponsor should be consulted by the investigator for instruction on the proper handling of the participant.

Drug accountability will be assessed by documenting the quantities of drug used between study visits (tube counts and weighing). At the first clinic visit and subsequent study visits, the amount of study cream to be applied is to be determined by weighing a tube before and after the participant applies a thin film of study cream to the affected areas. Participants will be instructed to bring all study cream with them to the study visits in order for site personnel to assess study cream accountability.

6.5. Dose Modifications

Application adjustments/modifications (decrease or increase in study cream strength or frequency of application) are not allowed except for study cream interruption or permanent discontinuation if needed (eg, for management of an AE).

Temporary study cream interruption could be due to an AE during the VC or LTS periods or due to clearance of the AD lesions during the LTS period, as described in Section [6.1](#).

6.5.1. Criteria and Procedures for Application Interruptions and Adjustments of Study Cream

Safety concerns should be discussed with the sponsor immediately upon occurrence or awareness to determine whether the participant should continue or discontinue study treatment.

In some circumstances, it may be necessary to temporarily interrupt treatment as a result of AEs or laboratory abnormalities that may have an unclear relationship to study cream. In the event of an AE is present at a specific site of application, treatment may be temporarily withheld only at that lesional site and continued elsewhere. This should be recorded as a dose interruption on the AE eCRF page. Except in cases of emergency, it is recommended that any findings of concern (eg, AE) be confirmed and that the investigator consult with the sponsor medical monitor (or other representative of the sponsor) before interrupting study cream applications. Additionally, the investigator must obtain approval from the sponsor before restarting study cream.

Participants who experience a recurrence of the initial AEs upon restarting the study cream may need to permanently discontinue treatment with the study cream.

Participants should be closely monitored for the development of signs and symptoms of infection during treatment with the study cream and up to the safety follow-up visit. Study cream should be interrupted if a participant develops a serious infection, an opportunistic infection, or sepsis. Study cream application should not be resumed until the infection is controlled.

Instructions for application interruptions of study cream are outlined in [Table 9](#). Individual decisions regarding interruptions should be made using clinical judgment in consultation with the medical monitor (whenever possible), taking into account relatedness of the AE to the study cream and the participant's underlying condition.

Table 9: Guidelines for Interruption and Restarting of Treatment Applications if Adverse Event Is Deemed Related to the Study Cream

Adverse Event Related to Study Cream ^a	Action Taken
ANC < 750/ μ L (without fever); < 1000/ μ L (with fever)	
 Laboratory abnormalities should be confirmed with repeat testing within 48 hours whenever possible and immediate delivery of the laboratory results requested. Study cream applications must be interrupted. At the discretion of the investigator, after consultation with the sponsor, study cream application may be restored once these have resolved.
Any other Grade 3 or higher laboratory abnormality (eg, hemoglobin with the exception of asymptomatic elevations in triglyceride, cholesterol, or amylase)	
 Laboratory abnormalities should be confirmed with repeat testing within 48 hours whenever possible and immediate delivery of the laboratory results requested. Study cream applications must be interrupted. At the discretion of the investigator, after consultation with the sponsor, study cream application may be restored once these have resolved.
Any Grade 4 laboratory abnormality or AST or ALT ($> 20 \times$ ULN)	
 Laboratory abnormalities should be confirmed with repeat testing within 48 hours whenever possible and immediate delivery of the laboratory results requested. Discontinue study cream if laboratory abnormalities are confirmed.

^a In the opinion of the investigator.

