2.2.2. INCB 18424-102: Pharmacokinetic Pediatric Study

The pilot pediatric study (INCB 18424-102), an open-label, descending age (\geq 12 to 17 years, \geq 7 to $<$ 12 years, and \geq 2 to $<$ 7 years), and increasing treatment strength (0.5%, 0.75%, or 1.5%) trial, was conducted to explore primarily the safety of several treatment regimens with ruxolitinib cream. Although not a dose range-finding study, it showed that the efficacy and safety of ruxolitinib cream 0.75% and 1.5% BID were similar in this pediatric age population to that in adolescents and adults with AD.

The results of Study INCB 18424-102 indicate that ruxolitinib cream at the 0.5%, 0.75%, and 1.5% strengths was safe and well-tolerated when administered BID for 4 weeks to pediatric participants with AD (aged \geq 2 to 17 years). A summary of the results is listed below:

[figure not shown]
- There were no serious TEAEs or TEAEs with a fatal outcome. One participant (7.1%) in Cohort 6 (\geq 2 to $<$ 7 years; ruxolitinib 1.5% cream BID) had a treatment-related TEAE of decreased neutrophil count with onset on Day 9 that led to study cream discontinuation. The event was Grade 1 in severity and resolved after 49 days.
- The overall incidences of TEAEs were highest among participants \geq 12 to 17 years old (50.0% and 45.5% for Cohorts 1 and 2, respectively) and did not vary according to ruxolitinib cream strength. Treatment-emergent AEs were Grade 1 or 2 in severity with the exception of 2 Grade 3 events, tooth fracture and lip injury, in a participant in Cohort 3 (\geq 7 to $<$ 12 years; ruxolitinib 0.75% cream BID).

- The most frequently reported TEAEs overall were headache (5.6%), atopic dermatitis (reported as worsening, flares, or exacerbations of atopic dermatitis; 4.2%), and otitis media and upper respiratory tract infection (2.8% each).
- The incidence of application site reaction TEAEs was low: 1 participant (10.0%) in Cohort 1 (≥ 12 to 17 years; ruxolitinib 0.5% cream BID) had an event of application site urticaria, and 1 participant (7.1%) in Cohort 4 (≥ 7 to < 12 years; ruxolitinib 1.5% cream BID) had 2 events of application site pain (reported term: stinging sensation). All application site reaction TEAEs were Grade 1 in severity and resolved on the same day as the event onset.
- There were no clinically meaningful changes in mean chemistry or hematology parameters over time, and no clinically meaningful changes were noted for vital signs or height.

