6.5.2. Criteria for Permanent Discontinuation of Study Cream Due to an Adverse Event

The occurrence of unacceptable severity of an AE not caused by the underlying disease will be presumed to be related to study cream and will require that the study cream be permanently discontinued. Unacceptable severity is defined as follows:

- Occurrence of an AE that is related to treatment with the study cream that, in the judgment of the investigator or the sponsor's medical monitor, compromised the participant's ability to continue study-specific procedures or is considered to not be in the participant's best interest.
- Participant presents with a worsening of AD that requires treatment with a prohibited concomitant medication.
- Persistent AE requiring a delay of therapy for more than 2 weeks without resolution of the AE.
- Any Grade 4 laboratory abnormality related to the study cream (see [Table 9](#)).

See Section [7](#) for discontinuation procedures.

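### Table 9's restart wording covers related Grade 4 laboratory values that its own third row and Section 6.5.2 direct to discontinuation

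*Protocol*

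**What the plan says.** Table 9 (Protocol Section 6.5.1) tells sites what to do when a laboratory abnormality is judged related to the study cream. It has three rows.

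- Row 1 is triggered by an ANC below 750/µL without fever, or below 1000/µL with fever.
- Row 2 is triggered by "Any other Grade 3 or higher laboratory abnormality". Symptom-free rises in triglyceride, cholesterol or amylase are excepted.
- Row 3 is triggered by "Any Grade 4 laboratory abnormality or AST or ALT" above 20 × ULN.

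All three rows ask for repeat testing within 48 hours where possible. Rows 1 and 2 then require interruption and add: "At the discretion of the investigator, after consultation with the sponsor, study cream application may be restored once these have resolved". Row 3 says instead: "Discontinue study cream if laboratory abnormalities are confirmed".

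Three other places bear on the same results. The text of Section 6.5.1 makes sponsor approval a condition of any restart. Section 6.5.2 lists "Any Grade 4 laboratory abnormality related to the study cream" among the events of unacceptable severity that require permanent discontinuation, with a cross-reference to Table 9. Section 7.1.1 includes those events among the reasons for which treatment must be stopped.

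**The concern.** A table that tells sites when to interrupt and when to stop should lead from each result to one action. Here the triggers are nested: a phrase that takes in Grade 3 and above includes Grade 4, and an ANC threshold with no floor includes the lowest counts. A related Grade 4 value can therefore be looked up in a row that allows a restart and in a row that requires discontinuation.

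What is at stake is the handling of the most severe laboratory findings in children aged 2 to under 12 years. Hematology and chemistry are scheduled twice after baseline in the vehicle-controlled period (Weeks 2 and 8) and seven times on treatment in the long-term safety period (Weeks 12, 16, 24, 32, 40, 48 and 52), so the instruction stays in use for a year. Reporting depends on it too: SAP Section 9.2.2 tabulates events leading to interruption separately from events leading to discontinuation.

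**Working it through.** No sample size, power or error rate is involved, and the plan states no figure to reproduce. The check compares triggers and actions.

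**Step 1. Which Table 9 rows does each related result meet?**

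| Related result | Rows met | Actions given |
|---|---|---|
| Grade 3, not ANC, not an excepted analyte, AST and ALT not above 20 × ULN | 2 | Interrupt; restart possible |
| Grade 4, not ANC, not an excepted analyte | 2 and 3 | Restart possible; discontinue if confirmed |
| Grade 4 ANC | 1 and 3 | Restart possible; discontinue if confirmed |
| Grade 4 symptom-free triglyceride, cholesterol or amylase | 3 | Discontinue if confirmed |

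The second and third lines conflict. The ANC line does not need the CTCAE v5.0 cut-off for Grade 4, which the documents do not give. Row 1 has no lower limit, so if a Grade 4 ANC lies below 750/µL it is always in row 1; at any positive cut-off the lowest counts are in both rows. The last line has no conflict, and none of its three analytes is in the required panel (Protocol Table 11).

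**Step 2. Does the table rank the rows?** No. It has no precedence note. The word *other* in row 2 sets that row apart from the ANC row above it, not from the Grade 4 row below it.

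**Step 3. Do other sections settle it?** Section 6.5.2 requires permanent discontinuation for a related Grade 4 laboratory abnormality, and Section 7.1.1 repeats this as mandatory. Reading all the sections together gives one outcome for the two conflicting lines. The restart sentence in rows 1 and 2 still stands against that outcome, and the cross-reference in Section 6.5.2 sends the reader back to the table that contains it.

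**Step 4. Do the sections agree on the conditions?**

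| Condition | Table 9 | Elsewhere |
|---|---|---|
| Confirmation before discontinuing for Grade 4 | Required (row 3) | Not mentioned in Section 6.5.2 |
| Sponsor's role before restart | Consultation (rows 1 and 2) | Approval (text of Section 6.5.1) |

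The first mismatch has a practical edge. Repeat testing is asked for only where possible, so the two passages differ on a Grade 4 value that was never retested.

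**The case against.** The strongest reply is that the protocol already answers the question. Section 6.5.2 follows directly after the table, applies to the same related events, and is backed by Section 7.1.1. The rows can also be followed together: interrupt, retest, then discontinue if Grade 4 is confirmed. The restart sentence is permissive and need not override a directive. A site cannot restart alone either, because Section 6.5.1 requires sponsor approval. Most of this stands, and it limits the point to conflicting wording. It does not remove the conflict: rows 1 and 2 still offer a restart for values that row 3 and Section 6.5.2 direct to discontinuation.

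Three stronger readings are tempting, and the documents do not support them.

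- *Sites are free to act in opposite ways.* A restart after a related Grade 4 value would need the sponsor to approve it against its own Section 6.5.2.
- *The pilot pediatric study shows that the problem will arise.* One child in its youngest 1.5% cohort "had a treatment-related TEAE of decreased neutrophil count" and stopped the cream, but Section 2.2.2 records that event as Grade 1. It lies outside the Grade 4 overlap and says nothing about its frequency.
- *The primary endpoint is affected, because stopping treatment before Week 8 makes a child a nonresponder.* This needs a related Grade 4 value before Week 8, a restart approved contrary to Section 6.5.2, and a child who would otherwise respond. The only scheduled post-baseline draw before Week 8 is at Week 2. Protocol Section 10.4.1 and SAP Section 7.2.2 also word the nonresponder rule differently: the SAP text joins discontinuation to a missing Week 8 assessment.

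**Conclusion.** The point holds as an internal inconsistency in a safety instruction. For related Grade 4 laboratory values, including Grade 4 ANC, Table 9 contradicts itself, and its restart wording contradicts Sections 6.5.2 and 7.1.1. The practical risk is confined to a reader who works from Table 9 alone, and the sponsor-approval requirement reduces it further. The requirements on confirmation and on the sponsor's role also differ between passages.

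There is no effect on sample size, power or alpha, and no effect on the primary result can be claimed. The documents give no rate of Grade 4 laboratory values, so no frequency is assigned. The conclusion rests only on reading Grade 3 or higher as including Grade 4, and on the ANC row having no lower limit. Correction is still worthwhile because the text governs the most severe laboratory findings and costs very little to align.

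**What to change.** Rewrite the three rows of Table 9 so that they are mutually exclusive and each result leads to one action. Then reconcile the table with Sections 6.5.1, 6.5.2 and 7.1.1 on three matters: whether a restart is available for a Grade 4 value, whether discontinuation depends on confirmation (and what applies when no retest is obtained), and whether the sponsor must be consulted or must approve before a restart. Which action applies at which grade is for the sponsor's medical team to state; this review proposes none. The cost is revised table and cross-reference wording and a memo to sites. No SAP analysis needs to change.

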6.5.2. Criteria for Permanent Discontinuation of Study Cream Due to an Adverse Event

The occurrence of unacceptable severity of an AE not caused by the underlying disease will be presumed to be related to study cream and will require that the study cream be permanently discontinued. Unacceptable severity is defined as follows:

- Occurrence of an AE that is related to treatment with the study cream that, in the judgment of the investigator or the sponsor's medical monitor, compromised the participant's ability to continue study-specific procedures or is considered to not be in the participant's best interest.
- Participant presents with a worsening of AD that requires treatment with a prohibited concomitant medication.
- Persistent AE requiring a delay of therapy for more than 2 weeks without resolution of the AE.
- Any Grade 4 laboratory abnormality related to the study cream (see [Table 9](#)).

See Section [7](#) for discontinuation procedures.

6.6. Concomitant Medications and Procedures

All concomitant medications and treatments (including over-the-counter or prescription medicines, vitamins, vaccines, and/or herbal supplements) must be recorded in the eCRF. Any prior medication received up to 28 days before the first application of study treatment and any new or ongoing medication used during the study through 30 days after the last application of study treatment will be recorded in the eCRF.

Any addition, deletion, or change in the dose of these medications will also be recorded. Concomitant medications administered after 30 days after the last application of study treatment should be recorded for SAEs as defined in Section 9.3. Concomitant treatments/procedures that are required to manage a participant's medical condition during the study will also be recorded in the eCRF. The medical monitor should be contacted if there are any questions regarding concomitant or prior therapy.

6.6.1. Permitted Medications and Procedures

The following are permitted during the study:

- Participants may use bland emollients (except those containing urea, salicylic acid, or lactic acid) such as Eucerin® cream. Participants should continue to use the bland emollient/moisturizer in the same manner they did before entering the study and throughout the course of the study.
Note: Emollients should not be used within 4 hours before and 2 hours after application of study cream.
- Bathing during the study should be limited to once daily for no longer than 15 minutes and not within 2 hours following study cream application. During baths, tepid (not hot) water and mild cleansing agents (eg, Basis® bar or Dove®) should be used. (See Section 5.3 for swimming guidance.) Showers should be limited in time with warm water and mild cleansing agents used.
- If sunscreen is needed, a mineral-based sunscreen (such as zinc oxide- or titanium oxide-based) with SPF of at least 30 may be used not less than 4 hours before and at least 2 hours after study cream application.
- Participants may use nonsedating, over-the-counter antihistamines.

